Visual analog Pain scale
Pain medications consumed
Adverse clinical events including DVT, stroke, PE, surgical site infection, reoperation Name
Medical record number
Patient demographics (age, sex, weight, height, BMI)

Data Analysis Plan

Demographics will be reported using descriptives such as count data and percentages. Differences between groups at baseline (pre-op) will be reported using two-tailed independent ttests for continuous variables, and chi-square or Fisher's Exact tests for categorical data, as appropriate.

The primary outcomes of range of motion, leg circumference, and pain ratings will be compared post-op between conditions using two-tailed independent t-tests. Should clinically relevant

demographics differ significantly between conditions pre-op (baseline), post-op comparisons will instead be conducted using one-way ANCOVAs controlling for differences at pre-op (baseline). These comparisons will additionally be made at multiple additional time-points throughout a 12- week post-op time period.

A priori power analyses were calculated for two-tailed independent t-tests for each primary outcome, using an alpha of .05, power = .80. Each of these are reported and the average of these numbers is used to calculate the final sample size. Clinically significant reductions in pain are defined as a 2-point change with a standard deviation of 2.5 using a 10-point scale; 84 patients were estimated. Clinically significant changes in range of motion are defined as: 10 degrees of difference from a 0-140 degree estimated range of values. Clinically significant changes in leg circumference are defined as: 1 cm difference in leg circumference using a 15-30 estimated range of values. To identify medium effect sizes of .55, 106 patients were estimated. Averaging these values, 99 patients were estimated. To ensure equal numbers of patients in each condition, 100 patients will be recruited for this study.

Risks to Research Participants

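### The 84 patients given for pain do not follow from their stated inputs (which need 52), and averaging sets N below the plan's own 106 for range of motion and circumference

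*Combined protocol and SAP*

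**What the plan says.** All of this is in the Data Analysis Plan section of the combined protocol and SAP, except the group size.

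- Three outcomes share primary status and one method: "The primary outcomes of range of motion, leg circumference, and pain ratings will be compared post-op between conditions using two-tailed independent t-tests".
- The power analyses are said to have been run "for each primary outcome, using an alpha of .05, power = .80".
- Pain: "2-point change with a standard deviation of 2.5 using a 10-point scale; 84 patients were estimated".
- Range of motion: "10 degrees of difference from a 0-140 degree estimated range of values". No SD is given.
- Circumference: "1 cm difference in leg circumference using a 15-30 estimated range of values". No SD is given.
- Effect size and the resulting average: "To identify medium effect sizes of .55, 106 patients were estimated. Averaging these values, 99 patients were estimated".
- Combining rule: "Each of these are reported and the average of these numbers is used to calculate the final sample size".
- Final number: "To ensure equal numbers of patients in each condition, 100 patients will be recruited for this study". Study Procedures puts 50 in each group.

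No allowance for dropout is stated, although the section on withdrawal lets patients leave at any time.

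**The concern.** The paragraph gives enough to check the pain figure, and the check fails by a wide margin: 84 is 62% above what the stated difference, SD, alpha and power require. So one of the three numbers behind N = 100 cannot be reproduced.

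The combining rule is a separate problem. If each primary outcome is meant to have 80% power, N has to meet the largest requirement. An average falls short of it whenever the requirements differ. Surplus power for pain does nothing for range of motion or circumference.

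The two problems are linked, because the unreproducible 84 feeds the average. As written, the paragraph does not settle what effect the pain calculation assumed, and it does not report what power 100 patients give for any primary outcome. That matters most when a null result on range of motion or swelling has to be interpreted.

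**Working it through.** **Method.** Two-sample t-test, noncentral t distribution, two-sided alpha .05, equal arms, complete follow-up. Effect size d = difference / SD. The required n per arm is the smallest n whose power reaches .80.

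**1. The plan's figures that reproduce**

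- d = .55: 52 per arm gives 79.3% and 53 per arm gives 80.1%, so N = 106. This matches the plan.
- The average: (84 + 106 + 106)/3 = 98.7, rounded up to 99. This matches. Averaging 84 and 106 once each gives 95, which does not. So 106 was counted twice, once each for range of motion and circumference.

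**2. The pain figure**

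d = 2/2.5 = 0.80.

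| n per arm | Total | Power at d = 0.80 |
|---|---|---|
| 25 | 50 | 79.2% |
| 26 | 52 | 80.7% |
| 41 | 82 | 94.7% |
| 42 | 84 | 95.2% |
| 50 | 100 | 97.7% |

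At the stated 80% power the requirement is 52. The plan's 84 is 84/52 = 1.62 times that.

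What would give 84:

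- Keep 2 points, SD 2.5 and two-sided alpha .05: 84 is exactly the minimum for 95% power.
- Keep 80% power: 84 is the minimum only for d from 0.619 to 0.626. That means SD = 2/d = 3.19 to 3.23 for 2 points, or a difference of 2.5d = 1.55 to 1.57 points with SD 2.5.
- Inflate 52 for dropout: 52/(1 − 0.38) = 83.9, so about 38% loss would be needed. No dropout rate is stated.
- Inflate for a rank test: 54 to 60 in total, still well short of 84.

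The documents do not show which figure is wrong: the 84, the SD, the difference or the power.

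**3. What 100 patients deliver**

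| Outcome | Assumed d | Power at 50 per arm |
|---|---|---|
| Range of motion | .55 | 77.7% |
| Circumference | .55 | 77.7% |
| Pain, if 2 points and SD 2.5 are right | 0.80 | 97.7% |
| Pain, if 84 at 80% power is right | 0.619 to 0.626 | 86.5% to 87.3% |

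The shortfall for the first two is 80 − 77.7 = 2.3 points. The d detectable with 80% power at 50 per arm is 0.566 instead of .55.

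**4. The link between the two errors**

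With 52 for pain, the plan's own rule would give (52 + 106 + 106)/3 = 88. Meeting every primary outcome's requirement would give 106. So 100 follows from neither.

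**5. Where d = .55 comes from**

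It cannot be derived from 10 degrees or 1 cm without an SD. Working backwards, it implies SDs of 10/.55 = 18.2 degrees and 1/.55 = 1.82 cm. On those SDs the detectable differences at 50 per arm are 0.566 × 18.2 = 10.3 degrees and 0.566 × 1.82 = 1.03 cm. These figures only restate the ratio .566/.55. They are not independent evidence that the trial can detect 10 degrees or 1 cm.

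**The case against.** The strongest reply is that the consequences are slight. The pain error is conservative: on the stated inputs, 100 patients give 97.7% power. The averaging is declared openly, anyone can see that 100 is below 106, and the cost is 2.3 points of power. This stands, and it is why the point concerns wording and not enrolment.

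The 84 also has an obvious candidate explanation. It is exactly the 95% power answer for 2 points and SD 2.5, and a reader should look there first. But the paragraph says .80, so this remains a guess until the sponsor confirms it.

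The text ties 106 to effect sizes of .55 without naming the outcomes, so applying it to both range of motion and circumference is an inference. It is a strong one: 106 follows directly after those two definitions, and 99 reproduces only if 106 is counted twice.

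The most substantial objection runs the other way. If d = .55 is unsourced, calling the shortfall small rests on an unverified number. That is fair. The implied SDs are the stated ranges divided by 7.7 (140/18.2) and 8.25 (15/1.82). If the SDs were instead a sixth to a quarter of the range (my assumption, for illustration), power at 50 per arm would be about 56% to 29% for range of motion and 51% to 26% for circumference. Loss to follow-up would also lower it: at d = .55, an assumed 10% or 20% loss leaves about 73% or 68%. So the 78% figure must carry its conditions. None of these objections makes 84 agree with its inputs, or makes an average meet the larger requirements.

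**Conclusion.** The concern holds. The pain requirement is 52 on the stated inputs, against the 84 reported. The averaging rule leaves two of the three primary outcomes at 77.7% power against a stated .80, for one two-sided t-test at alpha .05 with 50 per arm.

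The 77.7% assumes d = .55 and no loss to follow-up. On that basis the shortfall is minor and does not by itself call for more patients. Whether 100 is enough to detect 10 degrees or 1 cm cannot be confirmed, because no SDs are given. The point should be fixed, since the stated justification for N does not hold together, but it does not threaten the design.

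**What to change.** Reword the power paragraph and keep N = 100:

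1. Remove averaging as the basis for N. State instead the power that 50 per arm gives: about 78% for range of motion and for circumference if d = .55, plus the pain figure from step 2. Say that these assume complete follow-up.
2. Reconcile the 84. If 2 points, SD 2.5 and 80% power are right, replace it with 52 and quote about 98% power for pain. If the power was 95%, say so; 84 then stands, and pain power at 100 patients is still about 98%. If the SD or the difference is wrong, correct it and quote the matching power (about 87% if d is about 0.62). Report only the version that applies.
3. Give the SDs for range of motion and circumference with their source, and derive d from them. Failing that, label d = .55 as an assumption not derived from 10 degrees or 1 cm.

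The cost is one paragraph of text. Enrolment and analysis do not change. The only downside is that the stated power for two primary outcomes drops slightly below the .80 target.

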Patients will be approached in the office setting after it has been determined that they have failed conservative management of advanced knee arthritis. Patients will be in the surgeons' clinic behind closed doors with the performing surgeon and another member of the research team. Consent will be obtained in the office after scheduling total knee arthroplasty procedure. The consent process is expected to take 30 minutes, but more time is available to ensure that patients have all their questions answered prior to signing the consent form.

Sharing of Results with Research Participants

- Results will not be shared with research participants
- Results will not be shared with research participants' doctors

Study Design

Prospective randomized control cohort study

Study Procedures

Patients will be enrolled in study prior to surgery, outlined above in the consent process.

At the time of patient enrollment, A trained member of the research team will measure the circumference of the patient's leg at the mid-thigh, mid-knee and mid-calf with the leg in full extension. The patient's range of motion of the operative leg will be measured in flexion and extension. The patient will also fill out a baseline Western Ontario and McMaster Universities Osteoarthritis Index (WOMAC) Questionnaire. All measurements and questionnaire answers will be recorded on the study data collection sheet and will be transferred to RedCAP. At this time, patient's will be assigned a unique study identifier which will be randomly assigned to the experimental or control group. Unique study identifier numbers will start at "#1" and will go up by one additional number with every patient enrolled in the study. Even numbers will be assigned to the control group and odd numbers will be assigned to the study group, ending with 50 people enrolled in each group.

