Patients will be monitored for allergic reactions and over compression leading to tourniquet effect. There is potential for the experimental garment to not be as effective as the TED hose, which would potentially increase swelling. There is risk of discomfort while wearing the experimental or standard of care garment. Breach of confidentiality is always a concern anytime there is large amounts of patient data being collected, but the risk is being minimized by use of locked storage cabinets for hard copy data and RedCAP for electronic recording of data. There are no perceived psychological, social, legal or economic risks associated with participation in the study. All normal post-operative complications and risks still apply to patients undergoing TKA. Risks associated with the use of the experimental device are expected to be incredibly rare, minor, short lived and completely reversible.

Provisions to Protect the Privacy Interests of Research Participants

Consent will be obtained in a private room at an outpatient clinic facility with solid doors. Consent will be done one-on-one with patients and with another trained members of the research team present in the room.

Potential Benefit to Research Participants

If sleeve is found to be an effective adjunct to decreasing swelling and increase knee ROM, patients will likely have less pain post-operatively and have potential for increased range of motion. If pain is better improved, patients may use less narcotic pain medication which could reduce risk of developing opioid dependence. Patient participation in the study has the potential to benefit society.

Withdrawal of Research Participants

Patients are able to withdraw from the study at any point in time. If this occurs we will use the data we have recorded if possible and the patient will be included in the withdrawn numbers of the study.

Alternatives to Participation

Patients are still free to undergo TKA without needing to participate in the study using the SOC gradient compression dressing

Costs to Research Participants

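### The 84 patients given for pain do not follow from the stated inputs, which need 52, and the 84 feeds the averaged total of 99

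*Combined protocol and SAP*

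**What the plan says.** The sample-size paragraph of the Data Analysis Plan sets one method for all primary outcomes: "A priori power analyses were calculated for two-tailed independent t-tests for each primary outcome, using an alpha of .05, power = .80". For pain it then gives "a 2-point change with a standard deviation of 2.5 using a 10-point scale; 84 patients were estimated".

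For range of motion and leg circumference it gives clinically relevant differences and a range of values, but no SD. One figure follows: "To identify medium effect sizes of .55, 106 patients were estimated". The per-outcome numbers are combined by a rule under which "the average of these numbers is used to calculate the final sample size", with the result "Averaging these values, 99 patients were estimated". This is raised to 100 so that the groups are equal, and Study Procedures confirms 1:1 allocation, "ending with 50 people enrolled in each group".

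The protocol states no dropout allowance, multiplicity adjustment or non-parametric correction that would enlarge the pain figure.

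**The concern.** A 2-point difference with an SD of 2.5 is a large standardised effect, 0.80. The number given for it, 84, is not far below the 106 given for an effect of .55, although both are said to use the same test, alpha and power. Required sample size varies roughly with the inverse square of the effect, so scaling the 106 gives about 106 × (.55/.80)² = 50 for pain.

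Two things are at stake. First, the pain figure enters the average that sets the size of the trial, so an irreproducible number is part of the justification for enrolling 100. Second, pain is a primary outcome, and the reading of a null result depends on what the trial could detect. The plan names 2 points as the target, but a reader cannot tell whether the 84 was really calculated for 2 points, with SD 2.5, or at 80% power.

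**Working it through.** **Inputs** (Data Analysis Plan; allocation from Study Procedures): two-sample t-test, two-sided alpha .05, power .80, 1:1 allocation; pain difference 2 points, SD 2.5; effect size .55 for the figure of 106.

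**Method.** Power comes from the noncentral t distribution with 2n − 2 degrees of freedom and noncentrality d·√(n/2), where d = difference/SD and n is the number per arm. The required n is the smallest that reaches the target power.

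**Step 1: the plan's other figure reproduces.** For d = .55, power is .793 at 52 per arm and .801 at 53 per arm. So 2 × 53 = 106, as stated.

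**Step 2: the pain figure does not.** d = 2/2.5 = 0.80. Power is .791 at 25 per arm and .807 at 26 per arm. So 2 × 26 = **52**, against 84 stated. The normal approximation gives 50.

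**Step 3: what would give 84?** Changing one input at a time:

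| Change | Total N |
|---|---|
| Power .90 | 68 |
| Power .95 (41 per arm .947; 42 per arm .952) | **84** |
| SD about 3.20 to 3.23, power .80 | **84** |
| Difference about 1.55 to 1.56 points, SD 2.5, power .80 | **84** |
| One-sided test | 42 |
| Alpha .025 | 62 |
| Alpha .05/3 | 70 |
| Alpha .005 | 88 (84 by normal approximation) |
| Mann-Whitney inflation (efficiency .864) | 62 |
| 2:1 allocation (normal approximation) | 57 |
| SD × √2 | 102 |
| 52 inflated for 38% dropout | 84 |

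The SD and difference rows follow from the effect detectable with 42 per arm at 80% power, d = .619: 2/.619 = 3.23 and .619 × 2.5 = 1.55.

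**Step 4: the effect on the planned size.** (84 + 106 + 106)/3 = 98.7, which rounds to the stated 99. (84 + 106)/2 = 95 does not. So the 84 enters the total, apparently with 106 counted once each for range of motion and circumference. With 52 in its place, (52 + 106 + 106)/3 = 88.

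**Step 5: power at 50 per arm, complete data.** The effect detectable with 80% power is d = .566.

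| Case | Power | Detectable at 80% |
|---|---|---|
| Pain, 2 points, SD 2.5 (d = .80) | 97.7% | .566 × 2.5 = 1.41 points |
| Pain, 2 points, SD 3.23 (d = .619) | 86.6% | .566 × 3.23 = 1.83 points |
| d = .55 | 77.7% | – |

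The protocol allows withdrawal at any time but gives no rate. If 10% were lost (an assumption; 45 per arm), power would be 96.4% for 2 points at SD 2.5 and 73.2% for d = .55. At 88 patients with complete data (44 per arm), d = .55 would have 72.3%.

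**The case against.** The strongest reply is that the error does no harm to pain. The stated 84 exceeds the 52 needed, and 100 patients give ample power on the stated SD and more than 80% even at SD 3.23. Correcting the figure changes no patient, procedure or analysis. That stands, and it is why this is a matter of correction and not a shortfall.

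Three narrower points also stand in part:

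- The plan states its pain target plainly as 2 points, so the doubt is about which quantity behind the 84 is misreported, not about the absence of a target.
- Counting 106 twice is an inference from the arithmetic. It is a good one, since the two-value average gives 95, but the plan does not say so, and the 88 rests on the same reading.
- Alpha near .005 or dropout of about 38% also comes to about 84. Neither is stated or likely, but the check should cover alpha and any unreported allowance.

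Finally, the power for d = .55 and the choice of an average over the largest number are a separate issue. They matter here only because a careless correction of the 84 would lower the total further. None of this makes 84 follow from the stated inputs.

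**Conclusion.** The concern holds. Difference, SD, alpha, power and sample size for pain are mutually inconsistent: the stated inputs need 52 patients, 32 fewer than the 84 given. The conclusion assumes only what the plan states, namely a two-tailed independent t-test, alpha .05, power .80 and equal groups, and the same calculation returns the plan's 106 exactly.

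The exact match at 95% power makes that a natural explanation, but the protocol does not establish it; a larger SD or a smaller difference fits equally well. The consequence is that the basis for 99, and so for 100, cannot be traced. The finding does not show that the trial is too small for pain. It should be corrected, and confidence in it is high.

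**What to change.** Go back to the original calculation and establish which item is misreported: difference, SD, alpha, power, an unstated allowance, or the number itself. Correct that item from the record; do not choose a value because it fits 84.

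- If 2 points and SD 2.5 stand, either restate pain as 52 at 80% power, or label 84 as 95% power and amend the sentence that gives .80 for every outcome.
- If the SD was about 3.2, correct the SD and keep 84.
- If the difference was about 1.55 points, correct the difference and keep 84.

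Do not re-apply the averaging rule to reduce the total to 88. Keep 100 and state the power it gives for each outcome, noting that complete data are assumed: for pain, about 98% for 2 points and 80% for about 1.4 points if SD 2.5 is confirmed; for d = .55, about 78%, not 80%.

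The cost is one check of the original calculation and a correction of one or two sentences. The pain correction itself changes no patients or procedures.
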